### 9.4.2.2. Supplementary Analyses

The ANCOVA analysis as described for this endpoint will be repeated using the absolute (rather than the percent) change from baseline in the glucocorticoid total daily doses (in  $mg/m^2/day$ ) captured in the glucocorticoid concomitant medication eCRF at baseline and Week 28. All conventions used in the primary analysis of this endpoint will be used in this supplementary analysis.

The ANCOVA analysis (as described above) for the primary analysis of the second key secondary endpoint will be repeated using the Week 28 data without setting glucocorticoid dose reductions to 0 due to loss of androstenedione control. That is, all observed and multiply imputed GC dose data at Week 28 will be used regardless of the subject's androstenedione values. Missing data at Week 28 will be imputed using the same methods as in the primary analysis of this endpoint.

The ANCOVA analysis for the primary analysis of the second key secondary endpoint will be repeated with a modification to the androstenedione control criteria, with androstenedione control being defined as  $\leq 150\%$  of the baseline value or  $\leq ULN$ , according to sex and either age (for Tanner stage 1) or pubertal stage (for Tanner stages 2 to 5). Missing data at Week 28 will be imputed using the same methods as in the primary analysis of this endpoint.

The ANCOVA analysis for the primary analysis of the second key secondary endpoint will be repeated with a modification to the androstenedione control criteria, with androstenedione control being defined as  $\leq 180\%$  of the baseline value or  $\leq ULN$ , according to sex and either age (for Tanner stage 1) or pubertal stage (for Tanner stages 2 to 5). Missing data at Week 28 will be imputed using the same methods as in the primary analysis of this endpoint.

## 9.5. Analysis of Secondary Efficacy Endpoints

The following sections describe the secondary efficacy endpoints and methods of summarization and analysis. With the exception of the physiologic glucocorticoid daily dose responder analysis (see Section 9.5.1), missing data will not be imputed and only observed cases will be used for analyses of secondary efficacy endpoints. All p-values produced from the analyses in this section will be considered nominal p-values and will not be adjusted for multiplicity.

#### 9.5.1. Physiologic Glucocorticoid Daily Dose Responder Analysis

The achievement of a reduction in glucocorticoid daily dose to physiologic levels ( $\leq 11 \text{ mg/m}^2/\text{day}$  in hydrocortisone dose equivalent adjusted for BSA) at Week 28 while serum androstenedione is  $\leq 120\%$  of the baseline value or  $\leq ULN$  for sex and either age (for Tanner stage 1) or pubertal stage (for Tanner stages 2 to 5) is a secondary endpoint. The glucocorticoid daily dose and androstenedione values used in the derivation of this endpoint will follow the same conventions as described in Section 9.4.2. The primary analysis of this endpoint will be performed using a CMH test as described in Section 9.2.2. The CMH test will compare treatment groups and will include the stratification factors used in the randomization. Subjects whose androstenedione levels at Week 28 are not controlled will be considered non-responders. For subjects who are missing glucocorticoid dose, androstenedione, or both at Week 28, the multiply-imputed datasets from the second key secondary endpoint will be used to determine response.

Descriptive statistics will be presented by treatment group for the number and percentage of subjects classified as responders and non-responders at each postbaseline visit, using the same methods of determining androstenedione control as described above for Week 28. No data will be imputed at visits other than Week 28. For the Week 28 visit, the p-value from the CMH analysis will also be displayed.

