## 8.1. Subject Inclusion Criteria

To participate in this study, subjects must meet the following criteria:

- 1. Have documentation of witnessed written or oral pediatric assent from the subject deemed capable of providing assent, and written informed consent from the subject's parent(s) or legal guardian(s) (or the subject, if the subject has reached the age of majority) in accordance with the governing IRB/IEC and according to local laws and regulations.
- 2. Be a female or male 2 to 17 years of age with a body weight of at least 10 kg.
- 3. Have a medically confirmed diagnosis of classic CAH due to 21-hydroxylase deficiency based on standard medically accepted criteria such as elevated 17-OHP level, confirmed CYP21A2 genotype, diagnostic results after cosyntropin stimulation testing.
- 4. Be on a supraphysiologic glucocorticoid dose regimen defined as >12 mg/m²/day in hydrocortisone dose equivalents (see Section 9.3.2) that has been stable for at least 1 month prior to screening, is intended for chronic use, and consists ONLY of 1 or more of the following orally administered glucocorticoids: hydrocortisone, prednisone, prednisolone, or methylprednisolone. Subjects must be receiving a morning dose of glucocorticoid.
- 5. Have an A4 level (prior to the morning glucocorticoid dose) greater than the midpoint of the reference range, according to sex and either age (for Tanner stage 1) or pubertal stage (for Tanner stages 2 to 5).
- 6. Have a 17-OHP level (prior to the morning glucocorticoid dose) >2 × ULN according to sex and either age (for Tanner stage 1) or pubertal stage (for Tanner stages 2 to 5).
- 7. If treated with fludrocortisone, dose should be stable for at least 1 month prior to screening. Regardless of fludrocortisone treatment, upright plasma renin activity (PRA) (in the absence of medications that confound interpretation of PRA) during screening should be <3 × ULN and >lower limit of normal on the subject's usual sodium intake (if PRA >2 × ULN and <3 × ULN, subject must have normal age-specific systolic blood pressure and heart rate and serum potassium <ULN [Harman et al., 2011]).

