## 3.1. Randomization

Eligible subjects will be randomized 2:1 to either crinecerfont or placebo on Day 1 using an interactive response technology (IRT). Randomization will be stratified by pubertal stage (Tanner breast or genital stage 1 or 2 versus 3, 4 or 5) and sex.

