## **3.3.** Sample Size Considerations

The sample size of 81 subjects (54 in the crinecerfont treatment group and 27 in the placebo group) is based on a power calculation for the primary endpoint (change from baseline in serum androstenedione at Week 4). In the Phase 2 Study NBI-74788-CAH2001, the mean change from

Neurocrine Biosciences, Inc. Statistical Analysis Plan

baseline to Day 14 in androstenedione was -286.2 ng/dL with a standard deviation of 345.02 (pooled across dosing cohorts). Based on a 2-sample t-test with an effect size of 0.83, a sample size of 81 subjects will have greater than 90% power to detect a treatment difference at a 0.05 level of significance. With an effect size as small as 0.70, a sample size of 81 subjects will have greater than 80% power to detect a treatment difference at the same level of significance.

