# 6. GENERAL CONSIDERATIONS FOR DATA ANALYSES AND HANDLING

### 6.1. General Statistical Procedures

All analyses described in this plan are considered a priori analyses in that they have been defined prior to locking the study database for the Week 28 analysis. Analyses defined subsequent to locking the database will be considered post hoc analyses and will be applied as exploratory methodology. Any post hoc analyses will be statistically justified and described as appropriate in the CSR. Statistical analysis will be conducted, and all tables, figures, and listings generated using SAS® software (version 9.4 or later), unless stated otherwise.

Unless otherwise noted, data from the double-blind, placebo-controlled period (Day 1 to Week 28; "DB period") will be summarized by randomized treatment group, defined as crinecerfont or placebo (DB treatment group). Data from the open-label period (Week 28 to Week 52; "OL period") will be summarized by OL treatment group, defined as placebo/crinecerfont or crinecerfont/crinecerfont to describe the subject's randomized treatment assignment and their OL treatment, as well as all subjects combined. Note that while crinecerfont (and matching placebo) dose levels (25 mg bid via oral solution for subjects 10 to <20 kg, 50 mg bid via oral solution for subjects 20 to <55 kg, or 100 mg bid via oral capsules for subjects  $\geq$ 55 kg) are assigned based on weight at Day 1 and again at Week 28, summaries of the DB and OL period data will not be broken out by dose level unless otherwise specified.

Descriptive and inferential statistical methods will be used to evaluate and summarize the data from this study. The term "descriptive statistics" refers to the number of subjects (n), mean, median, standard deviation (SD) or standard error (SE), minimum, and maximum for continuous variables. Ordinal categorical data will be summarized using median, minimum and maximum values. Number and percentage of subjects will be summarized for categorical variables. The term "inferential statistics" refers to hypothesis tests that will be performed to assess differences between the treatment group and the control group. All hypothesis tests will be tests of the null hypothesis of no difference between the groups being compared versus the two-sided alternative hypothesis that there is a difference. The level of significance (type I error) for declaring statistical significance will be 0.05.

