The primary analysis of this endpoint will be performed using an ANCOVA model, as described in Section 9.2.1. The model will include treatment group, baseline glucocorticoid daily dose  $(mg/m^2/day)$ , and stratification factors used in the randomization.

Descriptive statistics will be presented by treatment group for the glucocorticoid total daily dose  $(mg/m^2/day)$  observed, change from baseline, and percent change from baseline values at baseline (observed data) and each postbaseline visit. Mean (±SEM) values of the glucocorticoid total daily dose at each visit will be summarized in line graphs by treatment group. Similar graphs will be presented for the change from baseline and percent change from baseline. These summaries will be presented for both the glucocorticoid total daily doses *without* the derivation of 0 for loss of androstenedione control as well as the glucocorticoid total daily doses *with* the derivation of 0 for loss of androstenedione control (for change from baseline and percent change from baseline summaries only).

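### The Week 28 responder test leaves out baseline glucocorticoid dose; adjusting for it would be a cheap improvement with a modest gain that depends on inputs the plan does not give

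*SAP*

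**What the plan says.** SAP 9.5.1 counts a child as a responder if the Week 28 dose is at or below 11 mg/m²/day in hydrocortisone equivalents and androstenedione is controlled. On the test it says "The primary analysis of this endpoint will be performed using a CMH test as described in Section 9.2.2" and "The CMH test will compare treatment groups and will include the stratification factors used in the randomization". The sample code in SAP 9.2.2 confirms that these factors are sex and pubertal stage, which gives four strata. No adjusted or supplementary analysis of this endpoint is planned. The Week 28 output is counts, percentages and the CMH p-value, with no treatment difference or confidence interval.

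Children missing dose or androstenedione take their response from the datasets imputed for the second key secondary endpoint. SAP 17.2 says how ANCOVA results are combined across the 100 datasets, but no rule is given for combining CMH results.

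For the percent change in dose, which uses the same doses and the same control rule, SAP 9.4.2 says "The model will include treatment group, baseline glucocorticoid daily dose" and the randomization factors. Protocol 8.1 sets the entry dose: "Be on a supraphysiologic glucocorticoid dose regimen defined as >12 mg/m²/day in hydrocortisone dose equivalents". It gives no upper limit. SAP 9.1 and 9.5 place the responder p-value outside the fixed sequence and call it nominal.

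**The concern.** The responder threshold is an absolute dose, and children enter anywhere above 12 mg/m²/day, so baseline dose determines how far each child must come down. Randomization is not stratified on it (SAP 3.1). With 27 placebo children, a chance imbalance in baseline dose can shift the responder difference, and this test does not correct for it. The covariate is already derived for SAP 9.4.2, so leaving it out gives up information that is in hand. What is at stake is the precision of one nominal secondary comparison and how easily it reads beside the adjusted analysis of the same doses.

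**Working it through.** **1. Inputs from the documents.** "The sample size of 81 subjects (54 in the crinecerfont treatment group and 27 in the placebo" group; "Eligible subjects will be randomized 2:1 to either crinecerfont or placebo on Day 1"; "The level of significance (type I error) for declaring statistical significance will be 0.05"; tests are made "versus the two-sided alternative hypothesis that there is a difference". The responder threshold is 11 mg/m²/day and entry is above 12.

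**2. The plan's own power figures.** These concern Week 4 androstenedione. The effect size is 286.2/345.02 = 0.83. For 54 against 27, √(1/54 + 1/27) = 0.2357, so the noncentrality is 0.83/0.2357 = 3.52, or 0.70/0.2357 = 2.97. The two-sided t-test then has power 93.6% and 83.5%, which agrees with the stated values above 90% and above 80%. The documents state no power for the responder endpoint.

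**3. How baseline sets the task.** The needed cut is 1 − 11/baseline:
- From 12.5: 1 − 11/12.5 = 12%, or 1.5 mg/m²/day.
- From 22: 1 − 11/22 = 50%, or 11 mg/m²/day.

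Protocol 7.2 describes up to four steps of about 1 to 4 mg/m²/day. At the largest step, 11/4 = 2.75, so the second child needs at least three steps and the first can need only one.

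**4. Assumed inputs.** Responder rates, baseline-dose spread and the link between baseline dose and response are not stated. The simulations below assume them. All compare the planned CMH test with a logistic score test that adds continuous baseline dose, in 54:27 trials with four strata.

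**5. Uncorrected gains.** Here baseline is 12 plus a gamma variable (mean 4.5, SD 3.5), percent change is normal by arm, and androstenedione control is drawn by arm, with 3000 trials per scenario. Null rejection was 4.0% for CMH and 5.7% for the score test, so part of the raw gain is a difference in test size. The critical values are 2.054 (4.0%) and 1.903 (5.7%), a difference of 0.151. CMH power moved to 5.7% size is Φ(Φ⁻¹(power) + 0.151). For example, 43% becomes Φ(−0.176 + 0.151) = 49%.

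| SD of percent change | CMH | Adjusted | Raw gain | CMH at 5.7% | Gain left |
|---|---|---|---|---|---|
| 12–15 points | 43% | 54% | 11 | 49% | 5 |
| 12–15 | 65% | 73% | 8 | 70% | 3 |
| 12–15 | 73% | 82% | 9 | 78% | 4 |
| 12–15 | 62% | 74% | 12 | 68% | 6 |
| 25 | 70% | 75% | 5 | 75% | 0 |
| 25 | 29% | 33% | 4 | 34% | −1 |

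This correction is rough, because it applies one pair of null rates to every row.

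**6. Direct calibration.** Setting each test to 5% under the same kind of model gave:
- Responders about 28% against 9%: raw 5 to 10 points fell to 1 to 3, at SD 12, 15 and 25 alike.
- About 36% against 11%, SD 12: raw 11 fell to 7.
- About 46% against 19%, SD 12 to 15: 7 to 10 remained.
- About 53% against 23%, SD 25: about 3.

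Two further sets, of six and four scenarios, gave calibrated gains of 1 to 7 and 1 to 8 points, positive in every case.

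**7. Dependence on prognostic strength.** In a separate logistic model, with CMH power about 64 to 82%, uncorrected gains by odds ratio per SD of baseline dose were:
- no association: 0.6 to 1.7
- 0.70: 1.9 to 2.5
- 0.50: 3.7 to 4.3
- 0.37: 4.3 to 6.9
- 0.22: 7.0 to 12.2

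Where CMH already had 94 to 98% power, the gain was 0.7 to 3.5. Null rates here were closer together (4.2 to 5.4% for CMH, 5.1 to 5.8% for the score test), and about one point of each gain is test size.

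**8. A coarser alternative.** Adding a median split of baseline dose to the CMH test gave about −3 to +9 points. It makes eight strata, with about 27/8 = 3.4 placebo children in each.

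**The case against.** The planned test is sound. It is stratified by the randomization factors and it held its error rate in simulation, whereas the asymptotic score test ran somewhat above 5%. With few placebo responders among 27 children, a logistic model can be unstable. Preferring a simple stratified test is a defensible choice between valid methods. The p-value is nominal and the trial is not sized on this endpoint. All of this stands.

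The plan is also not blind to baseline dose. SAP 9.4.2 gives the same doses a baseline-adjusted ANCOVA within the fixed sequence, with further ANCOVAs in 9.4.2.2, and SAP 7.3 tabulates baseline dose by arm. A reader might infer that an imbalance would go uncorrected everywhere. That is true of the responder test only.

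A reader might also infer that baseline dose largely decides who responds. The documents do not show this. Response also requires androstenedione control, and the dose cuts are guided by androstenedione at each step. The simulations that model the dose cut assume that the cut and androstenedione control do not themselves depend on baseline dose. What survives is that the needed cut depends on baseline by arithmetic, and that adjustment gave a positive gain in every directly calibrated scenario.

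**Conclusion.** This is a cheap, optional improvement to a valid analysis. The documents establish that the test omits baseline dose, that this dose fixes the needed cut, and that it is already a covariate for the continuous version of the outcome. They do not establish how much power is lost. Under assumed inputs the calibrated gain is roughly 1 to 10 points. It is largest when baseline dose is strongly prognostic, and about 1 to 3 points when percent change is highly variable or when responders are about 28% against 9%.

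A reader might take the raw simulated gains (4 to 12 points in the table) as a known loss. They rest on rates and spreads that the plan does not give, and part of them is the score test's larger size. Nor does the omission invalidate the CMH p-value or affect the fixed-sequence claims.

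**What to change.** Before database lock and unblinding for the Week 28 analysis, add to SAP 9.5.1:
- A logistic model with treatment, log baseline glucocorticoid dose (continuous), sex and pubertal stage.
- A covariate-standardised risk difference with 95% CI, estimated in each of the 100 imputed datasets and pooled. This also supplies the effect estimate and interval that the section lacks.
- A randomization-based p-value, because the asymptotic score test ran at about 5.5 to 6% under the null. State how it is obtained with imputed responses.
- The CMH test kept alongside, with its own rule for combining results across datasets, and a statement of which of the two is the main result.
- An exact or permutation fallback, with its trigger, if responders are sparse.

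The cost is a paragraph of SAP text and a few lines of code; no new data are needed. The downside is more modelling and one more rule to fix in advance. The p-value stays nominal, so fixed-sequence error control is unaffected. If the database is already locked, SAP 6.1 would make this a post hoc analysis, and it should be labelled so.

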#### 9.5.2. Body Mass Index

An additional secondary endpoint is the change from baseline in BMI SDS at Week 28 which will be analyzed using an ANCOVA model, as described in Section 9.2.1. Descriptive statistics and LS means for change from baseline to Week 28 in BMI SDS will be presented by treatment group along with the LS-mean treatment difference and p-value. Note that BMI SDS and BMI percentiles will be calculated based on the published CDC Growth Charts (ages 2 to 20 years) (Kuczmarski et al., 2002).

As a supplementary analysis, the change from baseline in BMI percentile at Week 28 will be analyzed using an ANCOVA model, as described in Section 9.2.1. Descriptive statistics and LS means for change from baseline to Week 28 in BMI percentile will be presented by treatment group along with the LS-mean treatment difference, 95% confidence intervals, and p-value.

Descriptive statistics will be presented by treatment group and visit for BMI SDS and BMI percentile observed and change from baseline values. Mean ( $\pm$ SEM) observed values at each visit will be summarized in line graphs by treatment group. Similar graphs will be presented for the change from baseline.

Shifts from baseline to Week 28 in BMI percentile categories will be presented in tables. The categories are defined as follows: underweight (BMI < 5th percentile), normal weight (BMI  $\ge$  5th percentile and < 85th percentile), overweight (BMI  $\ge$  85th percentile and < 95th percentile), and obese (BMI  $\ge$  95th percentile). Each shift table will have five rows and five columns, with rows reflecting the categories at baseline as well as missing values and columns reflecting the categories at Week 28 as well as missing values. A "Total" row and "Total" column will also be included. The number and percentage of subjects in each shift category will be displayed in the table; percentages will be based on the number of subjects included in the table.

In the subset of subjects classified as overweight or obese (where BMI  $\geq 85^{\text{th}}$  percentile is overweight and BMI  $\geq 95^{\text{th}}$  percentile is obese), the number and percentage of subjects achieving normal BMI (defined as BMI <  $85^{\text{th}}$  percentile) from baseline to Week 28 will also be presented by treatment group.

#### 9.5.3. Salivary 17-OHP

An additional secondary endpoint is the change from baseline in mean 24-hour salivary 17-OHP at Week 28. The salivary 17-OHP values collected at baseline and Week 28 will be averaged at each respective visit and analyzed using an ANCOVA model, as described in Section 9.2.1. Descriptive statistics and LS means for the change from baseline to Week 28 in mean 24-hour salivary 17-OHP will be presented by treatment group along with the LS-mean treatment difference, 95% confidence intervals, and p-value.

As a supplementary analysis, the percent change from baseline in mean 24-hour salivary 17-OHP at Week 28 will be analyzed using the same method as described in the primary analysis of this endpoint.

As a supplementary analysis, the change from baseline in mean morning salivary 17-OHP (average of 0600, 0800, +3 hours post-GC dose, and +6 hours post-GC dose values) at Week 28 will be analyzed using an ANCOVA model as described in Section 9.2.1. Descriptive statistics and LS means for change from baseline to Week 28 in mean morning salivary 17-OHP will be presented by treatment group along with the LS-mean treatment difference, 95% confidence intervals, and p-value.

Descriptive statistics will be presented for salivary 17-OHP by treatment group, visit, and timepoint from baseline through Week 28. For visits where pre-dose salivary 17-OHP is collected more than once (eg, Day 1; Week 4), the average of the pre-dose values will be analyzed. Otherwise, the pre-dose result is the single value collected. Observed and change from timepoint-matched baseline will be summarized.

Mean (±SEM) values of salivary 17-OHP at each visit will be summarized in line graphs by treatment group. Pre-dose values and visit average values will be presented on separate plots. Similar graphs will be presented for the changes from baseline.

The relationship between salivary and serum 17-OHP values will be depicted graphically. Scatterplots of salivary vs. timepoint-matched serum 17-OHP values will be generated by treatment group. The correlation coefficient, R, will be calculated and displayed in the scatterplots. A regression line will also be displayed on the scatterplots.

